1.1.3 Exploratory objectives

Other objectives are to explore other long-term treatment effects of ticagrelor vs. placebo on:

- Prevention of the composite of all-cause death, MI or stroke. The efficacy variable is time from randomisation to first occurrence of any event from the composite of all-cause death, MI or stroke
- Prevention of stroke. The efficacy variable is time from randomisation to first occurrence of stroke
- Effect on irreversible harm events, the composite of all-cause mortality, MI, stroke, intracranial haemorrhage and fatal bleeding. The efficacy variable is time from

randomisation to first occurrence of any event from the composite of all-cause mortality, MI, stroke, intracranial haemorrhage and fatal bleeding

- Prevention of the composite of arterial and venous thrombotic events that fulfills any SAE criteria. The efficacy variable is time from randomisation to the first occurrence of any event from the composite of arterial and venous thrombotic events that fulfills any SAE criteria (not included in CSP, see section 6)
- Prevention of coronary arterial revascularisations. The efficacy variable is time from randomization to the first occurrence of any coronary arterial revascularisation (not included in CSP, see section 6)
- Prevention of the composite of acute limb ischaemia (ALI) and major amputation of vascular aetiology. The efficacy variable is time from randomisation to first occurrence of any event from the composite of ALI and major amputation of vascular aetiology (not included in CSP, see section 6)
- Prevention of the composite of urgent peripheral arterial revascularisation, venous thrombotic event (defined as deep vein thrombosis [DVT] or pulmonary embolism), ALI and major amputation of vascular aetiology. The efficacy variable is time from randomisation to first occurrence of any event from the composite of urgent peripheral arterial revascularisation, venous thrombotic event, ALI and major amputation of vascular aetiology (not included in CSP, see section 6)
- Prevention of the composite of all-cause mortality, MI, stroke, ALI and major amputation of vascular aetiology. The efficacy variable is time from randomisation to first occurrence of any event from the composite of all-cause mortality, MI, stroke, ALI and major amputation of vascular aetiology (not included in CSP, see section 6)
- Prevention of the composite of CV death, MI, stroke, ALI, major amputation of vascular aetiology and venous thrombotic event. The efficacy variable is time from randomisation to first occurrence of any event from the composite of CV death, MI, stroke, ALI, major amputation of vascular aetiology and venous thrombotic event (not included in CSP, see section 6)
- Prevention of the composite of CV death, MI, stroke, ALI, major amputation of vascular aetiology and urgent peripheral arterial revascularisation. The efficacy variable is time from randomisation to first occurrence of any event from the composite of CV death, MI, stroke, ALI, major amputation of vascular aetiology and urgent peripheral arterial revascularisation (not included in CSP, see section 6)
- Prevention of the composite of all-cause mortality, MI, stroke, ALI, major amputation of vascular aetiology, venous thrombotic event, urgent peripheral arterial revascularisation and coronary revascularisation. The efficacy variable is time from randomisation to first occurrence of any event from the composite of all-

cause mortality, MI, stroke, ALI, major amputation of vascular aetiology, venous thrombotic event, urgent peripheral arterial revascularisation and coronary revascularisation (not included in CSP, see section 6)

- Health care resource utilisation and utilities assessed by Euro Quality of Life-5 Dimensions (EQ-5D) questionnaire to support health technology assessment and health economic modelling.

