2.4 Safety objective

The overall safety objective of this study is to assess the safety and tolerability of long-term therapy with ticagrelor compared to placebo in patients with T2DM at high risk of CV events, with or without background low-dose ASA therapy. Bleeding events will be analyzed using the Thrombolysis in Myocardial Infarction Study Group (TIMI), PLATO (PLATelet

inhibition and patient Outcomes), and the Bleeding Academic Research Consortium (BARC) definitions. Specific focus will be on:

- Time to first TIMI Major bleeding event (primary safety objective)
- Time to first TIMI Major or Minor bleeding event
- Time to first PLATO Major bleeding event
- Time to permanent discontinuation of study medication due to any bleeding event.

Non-serious AEs of interest (ie, dyspnoea, renal impairment, bradyarrhythmia, gout, and pneumonia), adverse events that leads to permanent discontinuation of study medication (DAEs) and all serious adverse events (SAEs) will be reviewed within the context of the earlier safety experience with the drug.

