5.6.5 Oral anticoagulants

Concomitant treatment with oral anticoagulant drugs (ie, vitamin K antagonists, direct thrombin inhibitors, factor X inhibitors) is not permitted during the study. If treatment with oral anticoagulant drugs is considered essential during the study, study medication must be discontinued, but should be resumed if oral anticoagulant therapy is stopped. Patients should continue to be followed as defined in Section 5.8.1.

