6.4.1.1 Adverse Events of interest

Secondary objectives will include an assessment of the long-term effects of ticagrelor on the following AEs of interest:

- Dyspnoea
- Renal impairment
- Bradyarrhythmia
- Gout
- Pneumonia.

Any other non-serious AE unless discontinuation of study medication due to AE (DAE) will not be collected in the study.

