3.2.3 Exploratory efficacy variables

Other efficacy variables are:

- Time from randomisation to first occurrence of any event from the composite of all-cause death, MI or stroke
- Time from randomisation to first occurrence of stroke
- Time from randomisation to first occurrence of any event from the composite of all-cause mortality, MI, stroke, intracranial haemorrhage and fatal bleeding (irreversible harm events)
- Time from randomisation to the first occurrence of any event from the composite of arterial and venous thrombotic events that fulfils any SAE criteria
- Time from randomisation to first occurrence of coronary arterial revascularisation
- Time from randomisation to first occurrence of any event from the composite of ALI and major amputation of vascular aetiology
- Time from randomisation to first occurrence of any event from the composite of urgent peripheral arterial revascularisation, venous thrombotic event, ALI and major amputation of vascular aetiology

- Time from randomisation to first occurrence of any event from the composite of all-cause mortality, MI, stroke, ALI and major amputation of vascular aetiology
- Time from randomisation to first occurrence of any event from the composite of CV death, MI, stroke, ALI, major amputation of vascular aetiology and venous thrombotic event
- Time from randomisation to first occurrence of any event from the composite of CV death, MI, stroke, ALI, major amputation of vascular aetiology and urgent peripheral arterial revascularisation
- Time from randomisation to first occurrence of any event from the composite of all-cause mortality, MI, stroke, ALI, major amputation of vascular aetiology, venous thrombotic event, urgent peripheral arterial revascularisation and coronary revascularisation
- Health care resource utilisation and utilities assessed by EQ-5D questionnaire to support health technology assessment and health economic modelling.

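### Three exploratory composites in the SAP count any DVT or pulmonary embolism, but the protocol collects these events fully only when they are serious

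*SAP*

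**What the plan says.** SAP 1.1.3 marks eight exploratory objectives as not included in the protocol. Three of them name a venous thrombotic event as a component:

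- The composite with urgent peripheral arterial revascularisation, acute limb ischaemia (ALI) and major amputation carries the definition: "venous thrombotic event (defined as deep vein thrombosis [DVT] or pulmonary embolism".
- The second is "Prevention of the composite of CV death, MI, stroke, ALI, major amputation of vascular aetiology and venous thrombotic event".
- The widest composite includes "major amputation of vascular aetiology, venous thrombotic event, urgent peripheral arterial revascularisation and coronary revascularisation".

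SAP 3.2.3 repeats all three. None has a seriousness limit. A fourth added endpoint in the same list does have one: the "composite of arterial and venous thrombotic events that fulfils any SAE criteria".

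On collection, Protocol 6.4.1.1 names five adverse events of interest, none of them venous, and then states: "Any other non-serious AE unless discontinuation of study medication due to AE (DAE) will not be collected in the study". Protocol 2.4 describes DAEs as "adverse events that leads to permanent discontinuation of study medication (DAEs". Protocol 6.4.3 has SAEs recorded from consent up to and including the study closure visit. Protocol 6.4.4.1 limits potential endpoint events to non-fatal MI, non-fatal stroke, death and bleeding. SAP 3.2 bases the efficacy objectives on events confirmed by the Clinical Endpoint Committee (CEC). Its only exception is vital status for all-cause death. SAP section 6 acknowledges the eight additions but names no new data source.

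**The concern.** The definition is wider than the collection rule. A result labelled as DVT or pulmonary embolism would in fact be serious events plus whichever non-serious events ended study treatment. That second part can be observed only in patients still taking study drug. If one arm stops treatment more often, fewer of its non-serious events are seen, and the comparison shifts slightly in that arm's favour.

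The SAP shows in its own list how to avoid this. The arterial and venous composite is restricted to events that meet SAE criteria, which matches what the protocol records. The three later composites in the list do not carry the restriction over.

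**Working it through.** The plan gives no venous event rate or serious share, so there is no figure to reproduce. The check sets the endpoint definition against the collection rules and then illustrates the size.

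**Step 1. Trace each kind of venous event to the database.**

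| Event | Route | Recorded? |
|---|---|---|
| Serious, on or off drug | SAE (Protocol 6.4.3); if admitted, also a discharge diagnosis (6.9.2) | Yes |
| Non-serious, on drug, leads to permanent stop | DAE | Yes |
| Non-serious, on drug, no permanent stop | None | No |
| Non-serious, after permanent stop | Cannot be a DAE | No |

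Row three matters because anticoagulation does not in itself make the event a permanent discontinuation. Under Protocol 5.6.5, "study medication must be discontinued, but should be resumed if oral anticoagulant therapy is stopped", and Protocol 5.8.1 lists the need for prohibited medication under temporary stops. Medication records do not fill the gap. Between randomisation and closure, Protocol 5.6.1 records only ASA, ADP receptor antagonists and drugs given around SAEs or potential endpoint events.

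**Step 2. Illustrate the size.** All inputs are assumptions:

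- n = share of venous events that are non-serious
- p = chance that a non-serious event on drug ends in a permanent stop
- d = share of follow-up on drug: 0.65 for ticagrelor, 0.75 for placebo

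Taking n and p as equal in both arms and venous events as spread evenly over follow-up:

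Capture = (1 − n) + n × p × d

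| n | p | Ticagrelor | Placebo | Ratio | Missed (ticagrelor / placebo) |
|---|---|---|---|---|---|
| 0.10 | 0.30 | 0.90 + 0.03 × 0.65 = 0.9195 | 0.90 + 0.03 × 0.75 = 0.9225 | 0.997 | 8.1% / 7.8% |
| 0.30 | 0.30 | 0.70 + 0.09 × 0.65 = 0.7585 | 0.70 + 0.09 × 0.75 = 0.7675 | 0.988 | 24.2% / 23.3% |
| 0.50 | 0.50 | 0.50 + 0.25 × 0.65 = 0.6625 | 0.50 + 0.25 × 0.75 = 0.6875 | 0.964 | 33.8% / 31.3% |

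These rows are not bounds. With n = 0.50 and p = 0.30, capture is 0.5975 versus 0.6125, so about 40% is missed and the ratio is 0.976. If d is equal in both arms the ratio is 1: events are still undercounted, but the comparison is not biased.

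**Step 3. Effect on a whole composite.** The ratio applies to the venous component alone. Two of the three composites also contain death, MI and stroke. If venous events were 10% of the total (assumption), the shift would be about 0.10 × (1 − 0.964) = 0.36% at the far end of the table and 0.10 × (1 − 0.997) = 0.03% at the near end.

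**Step 4. Effect of a seriousness limit.** With only SAEs counted, the n × p × d term disappears. The collection rule for the redefined endpoint is then the same on and off study drug.

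**Step 5. Check the adjudication rule.** Protocol 6.4.4.1 does not list non-fatal DVT or pulmonary embolism among the events sent to the CEC, while SAP 3.2 admits only confirmed events. Read literally, even a serious non-fatal venous event would not count. A seriousness limit alone does not resolve this.

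**The case against.** The strongest reply is that the gap may be small. An event need not involve admission to be serious: Protocol 6.4.2 includes important medical events that may need intervention to prevent a worse outcome, and Appendix B says these should usually be considered serious. An investigator could well report an outpatient DVT on that basis. Hospital discharge diagnoses are recorded, and fatal pulmonary embolism is classed as CV death (Protocol 6.3.1). This stands. It argues for the low end of the table, and it means one cannot assume that a DVT treated without admission goes unrecorded.

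Second, the meaning of DAE is not uniform. The objectives say permanent, but the abbreviation lists and Protocol 6.4.1.1 say only discontinuation. On the looser reading, a temporary stop for anticoagulation could count as a DAE. That would reduce the undercount but increase the dependence on drug status. With n = 0.30 and p = 1, capture is 0.70 + 0.30 × 0.65 = 0.895 versus 0.70 + 0.30 × 0.75 = 0.925, a ratio of 0.968.

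Third, if the CEC-only rule is applied literally, non-serious events recorded as DAEs would not count either, so the on-drug imbalance would not arise. That is correct, but it leaves the venous component with almost no countable non-fatal events, which can hardly be intended. The CEC charter and the eCRF are not among the documents and may supply a route.

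Finally, these endpoints are exploratory. SAP 4.1 treats their p-values and confidence intervals as measures of precision only. That stands and limits the importance of the point.

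**Conclusion.** The mismatch is real and minor. Three exploratory composites define their venous component more widely than the protocol collects it. Serious events are collected regardless of drug status; non-serious ones only through discontinuation while on drug. The amount missed is unknown: about 8% to 34% of venous events in the three scenarios tabulated, with a capture ratio of about 0.96 to 1.00. These figures rest entirely on assumed values of n, p and time on drug, and other values can fall outside the range.

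A reader might infer that the endpoint cannot be measured at all, or that its capture as a whole depends on being on study drug. The documents do not support either, because SAE recording continues to study closure in patients who have stopped treatment. A reader might also infer a demonstrated bias in favour of ticagrelor. That does not follow: the documents give no time on drug by arm, and the direction holds only if ticagrelor is stopped more often than placebo.

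The confirmatory sequence does not include these composites, so primary and secondary inference is unaffected.

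**What to change.** In SAP 1.1.3 and 3.2.3, define the venous component of the three composites as DVT or pulmonary embolism that fulfils any SAE criterion, matching the arterial and venous composite. In SAP 3.2, exempt these venous components from the CEC-confirmed-only rule by naming investigator-reported SAEs as their source, or cite the adjudication route if the CEC charter has one.

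The change is to SAP wording only and needs no new data. Its cost is that the few non-serious events recorded as DAEs no longer count, and the endpoint must be described as serious venous events.

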1.1.4 Safety objectives

The overall safety objective of this study is to assess the safety and tolerability of long-term therapy with ticagrelor compared to placebo in patients with T2DM at high risk of CV events, with or without background low-dose aspirin therapy. Bleeding events will be analysed using the Thrombolysis in Myocardial Infarction Study Group (TIMI), PLATO (PLATElet inhibition and patient Outcomes) and the Bleeding Academic Research Consortium (BARC) definitions. Specific focus will be on:

- Time to first TIMI Major bleeding event (primary safety objective)
- Time to first TIMI Major or Minor bleeding event
- Time to first PLATO Major bleeding event
- Time to permanent discontinuation of study medication due to any bleeding event.

Non-serious AEs of interest (i.e. dyspnoea, renal impairment, bradyarrhythmia, gout, and pneumonia), adverse events that leads to permanent discontinuation of study medication (DAEs) and all serious adverse events (SAEs) will be reviewed within the context of the earlier safety experience with the drug.

1.2 Study design

The study is event-driven and 19000 randomised patients are estimated to be required in order to collect 1385 adjudicated primary endpoint events. The anticipated maximal duration of treatment with study medication for an individual patient is 58 months. However, the actual duration of the study will be based on accrual of the pre-determined number of adjudicated primary endpoint events, and therefore the study may be shorter or longer than 58 months. The expected minimum follow-up period is 29 months and the expected average follow-up period is 40 months, based on an enrolment period of 28 months. A study closure plan will be developed that accounts for the patient recruitment pattern and the event rate to reach the predetermined number of adjudicated primary endpoint events (1385).

As safety is continuously monitored, the study may be terminated early if either a clear beneficial or harmful effect of the study treatment is detected during the Data Monitoring Committee (DMC) review.

1.3 Number of subjects

Based on clinical studies and epidemiological information, the event rate for the composite of CV death, MI or stroke has been estimated to be 2.5% annually in a population consisting of patients with T2DM at high risk for CV events without previous medical history of MI or stroke.

The final primary treatment comparison will be made at a significance level of 4.96% adjusted for the planned efficacy interim analysis. Assuming a true hazard ratio (HR) of 0.84 between ticagrelor and placebo, 1385 primary endpoint events will provide a power of 90%.

With an annual event rate of 2.5% in the placebo treatment group, 19000 patients, randomised in a 1:1 ratio, with an average follow-up period of 40 months, are estimated to provide the required number of primary events. The expected minimum follow-up period is 29 months, based on an enrolment period of 28 months.

The expected number of patients who will be lost-to-follow-up is negligible and hence not considered in the determination of samples size.

2. ANALYSIS SETS

2.1 Definition of analysis sets

2.1.1 Full analysis set (FAS)

All patients who have been randomised to study treatment will be included in the full analysis set (FAS) irrespective of their protocol adherence and continued participation in the study. Patients will be analysed according to their randomised study medication irrespective of whether the event occurred before or following discontinuation of study medication. Patients who withdraw consent to participate in the study will be included up to the date of their study termination except for vital status known through public records (for use in the analysis of all-cause death). All efficacy variables will be analysed using the FAS.

2.1.2 Safety analysis set

All patients who received at least 1 dose of randomised ticagrelor or placebo, will be included in the safety analysis set. Throughout the safety results sections, erroneously treated patients (e.g., those randomised to ticagrelor but actually given placebo) will be accounted for in the actual treatment group. A patient who in error has received both ticagrelor and placebo will be accounted for in the randomised treatment group.

2.1.3 Analysis set for U.S. Food and Drug Administration regulatory purposes

The primary analysis will be on the FAS in a subset of patients on acetylsalicylic acid (ASA) therapy at the day of randomisation visit.

2.2 Violations and deviations

Important protocol deviations will be summarised by treatment group and will include but not be limited to:

- Patients who were randomised but did not meet inclusion and exclusion criteria
- Patients who received prohibited concomitant medication
- Patients who received the wrong study medication at any time during the study
- Patients who were randomised but took no study medication.

Protocol deviations will be identified by programmed checks prior to database lock. However, as full analysis set (FAS) is the primary analysis set, protocol deviations will not imply exclusion from the analysis.

If one patient has been randomised more than once in the study, the patient will be analysed according to the first randomisation and all collected data will be reconciled at the discretion of the investigator.

Patients that were randomised at site 5730 will not be included in any analysis sets. AstraZeneca has reported the investigator to authorities for potential scientific misconduct and made the decision to exclude the patients from the analyses.

3. PRIMARY AND SECONDARY VARIABLES

3.1 Adjudication of clinical endpoint events

Clinical efficacy endpoint events and bleeding events will be evaluated by a Clinical Endpoint Committee (CEC) that is independent of the sponsor and investigators. Events will be identified using standard questioning of the patient at each visit, or by information the investigator may receive as part of standard medical practice. Safety endpoint events will be identified similarly. The investigator will complete endpoint event specific forms on the electronic case report form (eCRF) and compile additional source information into an 'Endpoint Package' which will be sent to the CEC for central adjudication.

3.2 Efficacy variables

The efficacy objectives will be evaluated using analysis of time from randomisation to first event, using only events positively adjudicated by the CEC (except for the analysis of all-cause death where also vital status known from public records will be used). Time will be calculated as the number of days plus one between the date of randomisation and date of the first occurrence of the event, or, if no event has occurred, the date of censoring (see Section 4.1.1).

When the first event is a MI or stroke, the time to the primary event will be the time to the MI or stroke, irrespective of whether or not the patient dies as a sequel of the event.

Deaths where cause of death is unknown will be accounted for as CV deaths in the efficacy analyses.

3.2.1 Primary efficacy variable

The primary efficacy variable is time from randomisation to first occurrence of any event from the composite of CV death, MI or stroke (ischaemic, haemorrhagic or unknown aetiology).

3.2.2 Secondary efficacy variables

Secondary efficacy variables are:

1. Time from randomisation to death of CV cause
2. Time from randomisation to first occurrence of MI
3. Time from randomisation to first occurrence of ischaemic stroke (including strokes classified as “Unknown type of stroke/No imaging performed”)
4. Time from randomisation to death of any cause.

